6.2 Treatment Regimens

The study is a Phase 2, multi-center, open-label, multiple cohort study of elotuzumab in combination with pomalidomide and low dose dexamethasone (EPd Cohort) and elotuzumab in combination with nivolumab (EN Cohort) in a 28 day cycle. The estimated duration of enrollment is 18 to 24 months, minimum of 24 months follow-up and study duration of about 48 months. This includes a up to 60 day screening period, a treatment period and a follow up period. The end of study will be defined as the date of the last visit of the last subject undergoing the study or death.

6.3 **Populations for Analyses**

The following subject populations will be used for the statistical analysis:

All Enrolled Subjects: All subjects who gave signed informed consent;

ITT Subjects: All enrolled subjects who meet the inclusion and exclusion criteria;

All Treated subjects: This population includes all subjects who receive at least one elotuzumab dose. The safety analysis set is also the all treated analysis set.

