4.5.2 Dexamethasone

Dexamethasone for subjects in the EPd cohort will be administered as indicated in Table 4.5.2-1.

Age	Day	1	8	15	22
Cycles 1 and 2					
\leq 75 years old	Dexamethasone (mg)	28 mg PO + 8 mg IV ^{a,b}			
> 75 years old	Dexamethasone (mg)	8 mg PO + 8 mg IV ^{a,b}			
Cycles 3 and beyo	ond				
\leq 75 years old	Dexamethasone (mg)	28 mg PO + 8 mg IV ^{a,b}	40 mg PO per week ^c	40 mg PO per week ^c	40 mg PO per week ^c
> 75 years old	Dexamethasone (mg)	8 mg PO + 8 mg IV ^{a,b}	20 mg PO per week ^c	20 mg PO per week ^c	20 mg PO per week ^c

Table 4.5.2-1:Dexamethasone Dosing, EPd Cohort

¹ On days of elotuzumab, infusion dexamethasone will be administered as a split dose of:

28 mg PO, for subjects \leq 75 years old or 8 mg PO for subjects > 75 years old (between 3 - 24 hours before the start of elotuzumab infusion)

8 mg IV (on the day of elotuzumab infusion at least 45 minutes before the start of infusion)

^b If elotuzumab dosing is skipped or discontinued, dexamethasone will be administered orally as in days without elotuzumab.

^c Note the dexamethasone dose, as elotuzumab is not given on Days 8, 15 and 22 of cycle 3 and beyond.

AND

At the investigator's discretion, the oral dexamethasone may be given as a split dose over 2 consecutive days. Dexamethasone delay should be performed as clinically indicated at the discretion of the investigator.

Dexamethasone for subjects in the EN cohort will be administered as indicated in Table 4.5.2-2.

Table 4.5.2-2:Dexamethasone Dosing: EN Cohort

Age	Day	1	8	15	22	
Cycles 1 and 2						
All subjects	Dexamethasone (mg)	8 mg IV ^{a,b}				
Cycles 3 and beyond						
All subjects	Dexamethasone (mg)	8 mg IV ^{a,b}				

^a On days of elotuzumab, dexamethasone will be administered as a premedication at dose of 8 mg IV at least 45 minutes before the start of infusion)

^b If elotuzumab dosing is skipped or discontinued, dexamethasone will be not be administered.

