4.5.4 Nivolumab

Nivolumab will be administered at a dose of 240 mg as an intravenous infusion over 30 minutes every 2 weeks (Days 1 and 15 of each 28 day cycle) during Cycles 1 through 4. Starting Cycle 5 and beyond, nivolumab will be administered at a dose of 480 mg as an intravenous infusion over 30 minutes every 4 weeks (Day 1 of each 28 day cycle).

Nivolumab should be administered before elotuzumab.

When administering Q2W, subjects may be dosed no less than 12 days from the previous dose. There are no premedications recommended for nivolumab on the first cycle.

Nivolumab can be delayed within a 3 day window of Day 1 and Day 15, during cycles 1 through 4, as long as the 12 day interval between 2 nivolumab doses is respected.

When administering Q4W, subjects may be dosed no less than 21 days from the previous dose. During cycles 5 and beyond, nivolumab can be delayed within a week.

Doses that fall outside the allowed window, regardless of the schedule, should be skipped.

Subjects should be carefully monitored for infusion reactions during nivolumab administration. If an acute infusion reaction is noted, subjects should be managed according to Section 4.5.6.

There will be no dose escalations or reductions of nivolumab allowed. Doses of nivolumab may be interrupted, delayed, or discontinued in accordance with Section 4.5.8 depending on how well the subject tolerates the treatment.

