8.2 Populations for Analyses

- The safety analysis set consists of subjects who receive at least one dose of study drug. The safety analysis set is also the all treated analysis set.
- The efficacy analysis set is the same as the all treated analysis set.

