7 STATISTICAL ANALYSES

7.1 General Methods

Continuous variables will be summarized using descriptive statistics; i.e. number of non-missing observations (n), mean, standard deviation (STD), median, minimum, maximum, first quartile

and third quartile. The number of decimal places displayed in all listings will be determined by the number of decimal places in the raw data. Unless otherwise specified, minimum and maximum will be reported to the precision as the data collected, one more decimal place for the mean and median, and two more decimal places for the standard deviation. The adjusted geometric mean, geometric mean ratio and the lower and upper limits of confidence interval will be displayed to three decimal places. Categorical variables will be summarized by frequencies and percentages.

Safety analyses will be conducted on all treated subjects. Efficacy analyses will be conducted on all treated subjects, and also by subgroups based on lines of prior therapy (2L, 3L), or by age group (<65 years, \geq 65 years), and (<75 years, \geq 75 years). Descriptive statistics (n, mean, median, standard deviation, minimum, maximum or interquartile range) will be provided. Because the sample size for the study is small, summary statistics with their associated 95% confidence intervals and tests of hypotheses will be based, to the extent possible, using small-sample statistics like the Clopper- Pearson for binomial data. Median time-to-event and its 95% confidence interval will be based on the Kaplan-Meier (KM) estimation procedure. The KM curves will be presented for time to event endpoints. Separate analyses will be conducted for each cohort EPd and EN.

Laboratory results, adverse events, and other symptoms will be graded using the National Cancer Institute (NCI) Common Terminology Criteria for Adverse Events (CTCAE), version 3.0, except where CTCAE grades are not available. Individual laboratory values will be presented in both the International System of Units (SI) and US unit (US). Adverse events will be categorized using the most current version of Medical Dictionary for Regulatory Activities (MedDRA), by system organ class and preferred term. Prior therapies will be summarized using the most current version of the World Health Organization (WHO) drug dictionary.

Statistical analyses will be carried out in SAS (Statistical Analysis System, SAS Institute, North Carolina, USA), unless otherwise indicated.

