7.3 Study Population

The intent-to-treat analysis set consists of enrolled subjects who meet the inclusion and exclusion criteria. The safety analysis set consists of subjects who receive treatment at least once. The safety analysis set is also the all treated subjects.

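### SAP 6.3 requires an elotuzumab dose for the all-treated set, against Protocol 8.2 and SAP 7.3, so a subject given another study drug but never elotuzumab would drop out of the safety and efficacy analyses

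*SAP*

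**What the plan says.** The documents define the treated population three times, in two different ways.

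- SAP 6.3, all treated subjects: "This population includes all subjects who receive at least one elotuzumab dose". The next sentence ties safety to the same group: "The safety analysis set is also the all treated analysis set".
- SAP 7.3: "The safety analysis set consists of subjects who receive treatment at least once". This too is equated with the all-treated subjects.
- Protocol 8.2: "The safety analysis set consists of subjects who receive at least one dose of study drug". That set is also called all treated, and "The efficacy analysis set is the same as the all treated analysis set".

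Protocol section 4 (Table 4.-1) counts nivolumab, pomalidomide and dexamethasone as study drugs along with elotuzumab.

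SAP 7.1 then applies the all-treated set to everything: "Safety analyses will be conducted on all treated subjects", and efficacy likewise. SAP 7.6.1 and 7.6.2 restrict the by-subject listings of adverse events, serious adverse events and events leading to discontinuation to the same set.

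On dose order, Protocol 4.5.4 says of the EN cohort: "Nivolumab should be administered before elotuzumab". In the EPd cohort, Protocol 4.5.2 places the oral dexamethasone "between 3 - 24 hours before the start of elotuzumab infusion". Protocol 4.5.1 places pomalidomide at least 2 hours after elotuzumab on days when both are given.

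**The concern.** An all-treated set should contain everyone exposed to the regimen. With elotuzumab scheduled after another study drug in both cohorts, there is an interval in which a subject has been exposed but does not yet meet the SAP 6.3 definition. A subject who stops in that interval, whether through an adverse event, intercurrent illness or a request to stop, and who never receives elotuzumab, is treated under the protocol and untreated under SAP 6.3.

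Two things are at stake. Any early adverse event in such a subject would be missing from the safety tables and also from the listings. And the denominator of the EN primary endpoint (ORR) would lose a subject who probably did not respond. In addition, two definitions under one name leave the choice of denominator open until data are available in an open-label study. Nothing marks the narrower definition as intended: the SAP document history does not mention it, and SAP 7.6.5 counts on-treatment laboratory tests from the first dose of any study therapy, which fits the protocol.

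**Working it through.** **Step 1. Who is classified differently.**

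| Subject received | Protocol 8.2 | SAP 7.3 | SAP 6.3 |
|---|---|---|---|
| Any elotuzumab, with or without other drugs | in | in | in |
| EN: nivolumab, never elotuzumab | in | in | out |
| EPd: oral dexamethasone, never elotuzumab | in | in | out |
| EN: dexamethasone premedication only | in, read literally | unclear | out |
| No study drug | out | out | out |

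Only subjects who never receive elotuzumab change status. Because pomalidomide follows elotuzumab on shared days, the planned order in EPd leaves mainly dexamethasone-only subjects.

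**Step 2. Reproduce the plan's figure.** SAP 5.2 and Protocol 8.1.2 give an exact interval of [0.15, 0.49] for a 30% ORR in 30 subjects, that is 9/30. The Clopper-Pearson limits for x responders in n are

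- lower = 0.025 quantile of Beta(x, n − x + 1)
- upper = 0.975 quantile of Beta(x + 1, n − x)

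With x = 9 and n = 30 these are Beta(9, 22) and Beta(10, 21), giving 0.1473 and 0.4940. The stated interval is reproduced.

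**Step 3. Change the denominator.** The number of subjects given another study drug but no elotuzumab is not in the documents. Assume 0, 1 or 2, all EN non-responders.

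| Excluded under SAP 6.3 | ORR | Exact 95% CI |
|---|---|---|
| 0 | 9/30 = 30.0% | 14.7% to 49.4% |
| 1 | 9/29 = 31.0% | 15.3% to 50.8% |
| 2 | 9/28 = 32.1% | 15.9% to 52.4% |

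Each exclusion adds about 1 percentage point. If the one excluded subject had instead responded, the result would be 8/29 = 27.6% (12.7% to 47.2%), a move in the other direction.

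**Step 4. Allow for replacement.** Screening continues until at least 30 are enrolled and treated. If treated is read as in SAP 6.3, the excluded subject would be replaced. The comparison is then 9/30 under SAP 6.3 against 9/31 = 29.0% (14.2% to 48.0%) under Protocol 8.2. The gap is again about 1 point.

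**Step 5. EPd cohort.** Take the plan's hazard λ = ln 2/15 = 0.0462 per month, and assume uniform accrual over 24 months with 24 months of further follow-up. The event probability is 1 − [exp(−24λ) − exp(−48λ)]/(24λ) = 0.8007. So 60 × 0.8007 = 48.0 events, matching the plan's 48, and 59 × 0.8007 = 47.2. The exact one-sample exponential test at one-sided 0.05, with medians of 11 and 15 months, has power 0.710 with 48 events and 0.702 with 47. The effect on EPd is negligible.

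**The case against.** The strongest reply is that this is a wording mismatch with little behind it. SAP 7.3 already carries the protocol's meaning, so exclusion is not certain. Such subjects would not vanish from the report either: SAP 7.3.1 tabulates all enrolled subjects by whether they were treated and lists membership of each population, SAP 7.5.2 lists survival for all enrolled subjects, and Protocol 6.1.1 collects serious adverse events from consent. The number affected may be zero.

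Much of this stands, and it limits the size of the point. It does not remove it. SAP 6.3 is the section that formally defines the populations, and a disposition table that called a nivolumab-exposed subject untreated would not replace that subject's adverse event record.

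Several stronger readings are tempting and are not supported.

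- *A nivolumab reaction, or taking dexamethasone first, excludes a subject.* It does not. Protocol 3.5 stops nivolumab alone after a Grade 3 or 4 nivolumab infusion reaction, and Protocol 4.5.8 lets the other drugs continue. Exclusion requires that no elotuzumab is ever given.
- *The excluded subjects are certain non-responders.* Protocol 4.5.8 regards patients continuing on nivolumab, pomalidomide or dexamethasone alone as still on study therapy, so a response is possible. Upward bias is likely, not assured.
- *Moving the lower limit from 14.7% to 15.3% changes a decision.* The EN objective is estimation, and no test or go/no-go rule is attached to 15%. Both limits round to the plan's 0.15. That 9/30 falls short of the stated bound above 15% is a separate sample-size matter.
- *The EN toxicity stopping rule would be distorted.* That rule is in Protocol 4.5.10, where the protocol's own definition of treated applies. The SAP contains no such rule.

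**Conclusion.** The point holds as an inconsistency in a governing definition. SAP 6.3 contradicts both Protocol 8.2 and SAP 7.3 and, followed as written, leaves out of the safety and efficacy analyses any subject exposed to another study drug who never receives elotuzumab. Whether anyone is actually left out is unresolved, because SAP 7.3 would keep the same subject.

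The expected size is small. It rests on an assumed 0 to 2 subjects, on their being EN non-responders, and on an illustrative count of 9 responders. Under those assumptions the ORR rises by about 1 percentage point per excluded subject, and some early safety events could go unreported in the main tables and listings. The EPd event count and power are essentially unaffected. The reason to act is that the safety set and the denominator of the EN primary endpoint should have one definition, settled before the data are analysed.

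**What to change.** In SAP 6.3, replace the elotuzumab requirement with the protocol's criterion, one dose of any study drug, so that SAP 6.3, SAP 7.3 and Protocol 8.2 agree. Two additions go with it:

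- State whether a subject in the EN cohort who received dexamethasone only as elotuzumab premedication counts as treated. Dexamethasone is a listed study drug but has no other scheduled role in that cohort, so the bare phrase does not settle the matter.
- Add a by-subject listing of anyone treated without elotuzumab, so that a reader can see whether the definition made any difference.

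Leave the time origin for PFS and OS at Cycle 1 Day 1. Moving it to the first dose of any study drug could shift EPd subjects back by a day, since the oral dexamethasone may be taken up to 24 hours before the infusion, and that would conflict with the Cycle 1 Day 1 anchoring in both documents.

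The cost is a few lines of SAP text and one short listing, with no new data and no change to the protocol.

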7 STATISTICAL ANALYSES

7.1 General Methods

Continuous variables will be summarized using descriptive statistics; i.e. number of non-missing observations (n), mean, standard deviation (STD), median, minimum, maximum, first quartile

and third quartile. The number of decimal places displayed in all listings will be determined by the number of decimal places in the raw data. Unless otherwise specified, minimum and maximum will be reported to the precision as the data collected, one more decimal place for the mean and median, and two more decimal places for the standard deviation. The adjusted geometric mean, geometric mean ratio and the lower and upper limits of confidence interval will be displayed to three decimal places. Categorical variables will be summarized by frequencies and percentages.

Safety analyses will be conducted on all treated subjects. Efficacy analyses will be conducted on all treated subjects, and also by subgroups based on lines of prior therapy (2L, 3L), or by age group (<65 years, \geq 65 years), and (<75 years, \geq 75 years). Descriptive statistics (n, mean, median, standard deviation, minimum, maximum or interquartile range) will be provided. Because the sample size for the study is small, summary statistics with their associated 95% confidence intervals and tests of hypotheses will be based, to the extent possible, using small-sample statistics like the Clopper- Pearson for binomial data. Median time-to-event and its 95% confidence interval will be based on the Kaplan-Meier (KM) estimation procedure. The KM curves will be presented for time to event endpoints. Separate analyses will be conducted for each cohort EPd and EN.

Laboratory results, adverse events, and other symptoms will be graded using the National Cancer Institute (NCI) Common Terminology Criteria for Adverse Events (CTCAE), version 3.0, except where CTCAE grades are not available. Individual laboratory values will be presented in both the International System of Units (SI) and US unit (US). Adverse events will be categorized using the most current version of Medical Dictionary for Regulatory Activities (MedDRA), by system organ class and preferred term. Prior therapies will be summarized using the most current version of the World Health Organization (WHO) drug dictionary.

Statistical analyses will be carried out in SAS (Statistical Analysis System, SAS Institute, North Carolina, USA), unless otherwise indicated.

7.2 Study Conduct

The study shall be conducted as described in approved protocol.

7.2.1 Accrual

The following will be presented on all enrolled subjects:

- Number of subjects accrued by investigational site
- Number of subjects accrued by month

7.2.2 Relevant Protocol Deviations

Eligibility and on-study deviations as required by guidelines will be summarized and listed for all treated subjects. A relevant protocol deviation is defined as a deviation from the protocol which is programmed in the database and which could potentially affect the interpretability of the study results.

• Subjects with relevant eligibility deviations:

- Subjects who have received 3 or more prior lines of therapy
- Subjects have no measureable disease at screening, based on central laboratory results, defined as one or more of the following
 - Serum IgG, IgA, IgM M-protein $\ge 0.5 \text{ g/dL}$
 - Urinary M-Protein ≥ 200 mg urinary M-protein excretion in a 24 hour collection sample
 - Involved serum free light chain (sFLC) ≥ 10 mg/dL provided the FLC ratio is abnormal.
- Subjects with on-study deviations:
 - Non-protocol specified systemic anti-myeloma therapy prior to discontinuation of study therapy
 - No baseline efficacy assessment. This occurs when there are no tumor assessments at all (laboratory assessments) on or prior to first day of dosing.

A by subject listing of relevant protocol deviations will be provided.

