3.3.1 Inclusion Criteria

1. Signed Written Informed Consent

- a) Subject is, in the investigator's opinion, willing and able to comply with the protocol requirements.
- b) Subject has given voluntary written informed consent before performance of any study-related procedure not part of normal medical care, with the understanding that consent may be withdrawn by the subject at any time without prejudice to their future medical care.

2. Target Population

a) All subjects must have documented disease progression per IMWG (Appendix 4) criteria during or after their last anti-myeloma therapy.

Revised Protocol No.: 03 Date: 08-Mar-2018

- b) As of Amendment 02, this criterion has been moved to criterion 2.i.i for clarity.
- c) As of Amendment 02, this criterion has been moved to criterion 2.i.ii for clarity.
- d) Per Amendment 1, this criterion is no longer applicable. Specifications previously listed in criterion d) have been included in the revised criterion c) above.
- e) Measurable disease at screening, based on central laboratory results, defined as one or more of the following:
 - i) Serum IgG, IgA, IgM M-protein $\ge 0.5 \text{ g/dL}$
 - ii) Urinary M-Protein \ge 200 mg urinary M-protein excretion in a 24 hour collection sample
 - iii) Involved serum free light chain (sFLC) \geq 10 mg/dL provided the FLC ratio is abnormal.
- f) ECOG Performance Status ≤ 2 (Appendix 2).
- g) Subject Re-enrollment: This study permits the re-enrollment of a subject that has discontinued the study as a pre-treatment failure (ie, has not been treated). If re-enrolled, the subject must be re-consented.
- h) As of Amendment 02, this criterion has been moved to criterion 2.i.iii for clarity.
- i) for the EPd Cohort:
 - i) Subjects must have received at least 1 but no greater than 2 prior lines of therapy (note: induction and stem cell transplants with or without maintenance therapy is considered 1 line of therapy)
 - Subjects must have received prior treatment with a lenalidomide-containing regimen for at least 2 consecutive cycles (full therapeutic dose) and must have been deemed as relapsed, refractory, or intolerant. Refractory is defined as progressing on-treatment or within 60 days of the last dose.³⁰

NOTE: lenalidomide-based regimens to which the subject has relapsed or been refractory to is not required to be the most recent regimen received.

- iii) Prior elotuzumab exposure is permitted only if subjects fulfill all of the following:

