 - (1).Did not discontinue elotuzumab due to any intolerable drug-related adverse reaction.
 - (2).Did not participate in a prior elotuzumab clinical trial, regardless of treatment assignment
- j) For EN Cohort:
 - i) Subjects must have received at least 4 prior lines of therapy including a proteasome inhibitor (PI), an immunomodulatory (IMID) agent, and an anti-CD38 antibody.

3. Age and Reproductive Status

- a) Males and Females, at least 18 years or legal age of consent per local regulations
- b) Women of childbearing potential (WOCBP) must have a negative serum or urine pregnancy tests (minimum sensitivity 25 IU/L or equivalent units of HCG), at 10-14 days prior to start of study drug; another within 24 hours prior to the start of study drug.
- c) Women must not be breastfeeding
- d) WOCBP must agree to follow instructions for method(s) of contraception for 1 month (4 weeks) before the start of treatment with study drugs, for the duration of treatment with study drugs, and for a total of 5 months post-treatment completion.

- e) Males who are sexually active with WOCBP must always use a latex or synthetic condom during any sexual contact with females of reproductive potential while taking pomalidomide and for up to 28 days after discontinuing pomalidomide, even if they have undergone a successful vasectomy. Male patients must not donate sperm.
- f) Azoospermic males and WOCBP who are continuously not heterosexually active are exempt from contraceptive requirements. However, they must still undergo pregnancy testing as described in this section.
- g) All subjects must be willing and able to comply with the local pomalidomide risk management program or the Pomalidomide Pregnancy Risk Prevention Plan
- h) All subjects must agree not to share study medication.
- i) Male subjects receiving elotuzumab or nivolumab must also agree to follow instructions for method(s) of contraception for 1 month (4 weeks) before the start of treatment with study drugs, for the duration of treatment with study drugs, and for a total of 7 months post-treatment completion.
- j) Subjects must be willing to refrain from blood donations during study drug therapy and for 90 days after therapy.

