5.2 EN Cohort

The planned sample size will be approximately 30 treated subjects; screening will continue until a minimum of 30 patients are enrolled and treated.

For a 30% observed ORR rate and a sample size of N=30 yields an exact confidence interval of [0.15, 0.49]. These design parameters ensure a lower bound higher than 15%.

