9.1 Topline Analyses

Study conduct:

• Relevant eligibility deviations (Table and Listing)

Subject population:

- End of Treatment Summary
- Demographic Characteristics Summary
- Response to Most Recent Line of Therapy Summary
- Time from Diagnosis to First Dose Date

Extent of exposure:

• Number of Cycles Summary

Tumor response:

Best Overall Response

Progression free survival:

- Currentness of Follow-Up for PFS (Inv) Summary
- Kaplan-Meier plot of PFS Primary) (Figure)
- Kaplan-Meier plot of PFS (Secondary) (Figure)

Overall survival :

- Currentness of Follow-Up for Overall Survival Summary
- Kaplan-Meier plot of overall survival (Figure)

Safety:

- Adverse Event Summary by CTC Grade Combined
- Serious Adverse Event Summary by CTC Grade Combined
- Adverse Event Leading to Discontinuation Summary by CTC Grade Combined
- Infusion Reaction Summary by Common Terminology Criteria
- Deaths
- Deaths within 60 days of last study drug
- On study Hematology Lab Results
- On study Chemistry Lab Results

Specific tables corresponding to these topics will be identified in a separate Data Presentation Plan.

Table 4:	Document Histo	bry
Version Number	Author(s)	Description
0.1		Original version
0.2		Upated upon BMS comments on draft 1
0.3		Upated upon BMS comments on draft 2
0.4		Upated upon BMS comments
0.5		Updated upon protocol amendment 01
0.6		Updated upon protocol amendment 01 & BMS comments
1.0		Updated upon protocol amendment 01 & approved
1.1		
1.2		Updated upon protocol amendment 02 & BMS comments that include updates on draft amendment 03. There fore the SAP may not be consistent with the protocol whilst the amendment 03 is being finalized.
2.0		Updated upon draft of protocol amendment 03 received on 12Feb2018.
2.1		Added protocol amend 03 into section 2.4.
		Changed "last evaluable assessment" to "last adequate tumor assessment"
		Added sample size section 5.2 for EN cohort per amend 03

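### SAP 7.2.2 applies an EPd-only prior-lines deviation rule to all treated subjects, so it flags EN subjects who are eligible under the current criterion and misses EN subjects with 0 to 2 lines

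*SAP*

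**What the plan says.** SAP 7.2.2 sets the scope of the deviation report: "Eligibility and on-study deviations as required by guidelines will be summarized and listed for all treated subjects". It defines a relevant deviation as a programmed departure from the protocol that might bear on how the results are interpreted. It then lists two eligibility items, neither with a cohort label. One is "Subjects who have received 3 or more prior lines of therapy". The other is absence of measurable disease at screening.

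The all-treated set in SAP 6.3 takes in both cohorts, since each receives elotuzumab: "This population includes all subjects who receive at least one elotuzumab dose".

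Protocol 3.3.1 sets opposite line requirements for the two cohorts. For EPd (2.i): "Subjects must have received at least 1 but no greater than 2 prior lines of therapy". For EN (2.j): "Subjects must have received at least 4 prior lines of therapy including a proteasome inhibitor (PI", and the sentence goes on to name an immunomodulatory agent and an anti-CD38 antibody. The synopsis and the EN research hypothesis (protocol 1.2.2) give the same EN population.

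SAP 9.1 puts the output among the topline analyses: "Relevant eligibility deviations (Table and Listing".

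**The concern.** The prior-lines item is the complement of the EPd upper limit, so it does its job in that cohort. Applied to EN it points the wrong way: having many prior lines is what qualifies a subject, and having few is the violation.

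At stake is whether a reader can tell from the deviation table if the EN subjects match the heavily pretreated population named in the EN hypothesis. EN is a single-arm cohort of about 30 with ORR as its primary endpoint, so one subject moves ORR by 1/30, or about 3.3 percentage points. Whether each subject belongs to the intended population is therefore useful to know, and the rule reports it wrongly. The baseline summary in SAP 7.3.2 does not fill the gap. It groups prior therapy as 2L or 3L, which leaves no category for an eligible EN subject. A reader would have to rebuild eligibility from the by-subject prior-therapy listing in SAP 7.3.4.

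**Working it through.** The plan gives no figure to reproduce. The check compares the SAP flag with protocol eligibility at each count of prior lines.

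Inputs:
- Flag (SAP 7.2.2): prior lines ≥ 3, in either cohort.
- EPd eligible on lines (protocol 3.3.1, 2.i): 1 or 2.
- EN eligible on lines (protocol 3.3.1, 2.j): ≥ 4.
- Planned treated subjects: about 30 EN (SAP 5.2, "The planned sample size will be approximately 30 treated subjects") and at least 60 EPd (SAP 5.1).

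| Prior lines | Flagged | EPd status | EPd result | EN status | EN result |
|---|---|---|---|---|---|
| 0 | no | ineligible | missed | ineligible | missed |
| 1–2 | no | eligible | correct | ineligible | missed |
| 3 | yes | ineligible | correct | ineligible | correct |
| 4 or more | yes | ineligible | correct | eligible | false flag |

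For EN the rule is right only at exactly 3 lines. Even there the summary count does not help, because that subject is added to the eligible subjects who are also flagged.

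Counts if every planned subject is eligible and all EN subjects fall under the current criterion:
- EN flagged: 30/30 = 100%.
- EPd flagged: 0/60 = 0%.
- Both cohorts together: 30/(30 + 60) = 33.3% listed as eligibility deviators, with no true violation.

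The 30/30 is an upper figure. The summary of key changes for Revised Protocol 03 records that the EN requirement on prior lines and therapy type was modified, and the documents do not give the previous requirement. Suppose m of the 30 EN subjects were enrolled under the current criterion and met it. Then m false flags are certain, and the flagged total lies between m and 30 depending on the line counts of the others. The documents do not give m.

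With the cohort-specific condition (EPd > 2, EN < 4), false flags among eligible EN subjects fall from 30/30 to 0/30 on the same assumption, and EN subjects with 0, 1 or 2 lines are caught.

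**The case against.** The strongest defence is that SAP 7.2.2 itself defines a relevant deviation as a departure from the protocol. An EN subject with 4 or more lines has not departed from it, so a careful programmer might never apply the item to EN. SAP 7.1 adds: "Separate analyses will be conducted for each cohort EPd and EN". The tables themselves are left to a Data Presentation Plan that is not part of these documents, and an EN table showing 100% deviators would be conspicuous. This makes a wholly wrong EN table a worst case and not a certainty, but it does not correct the text. Running the same rule separately within EN still gives the wrong answer, and no EN-specific item exists to replace it.

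The SAP document history does warn of possible inconsistency with the protocol, but in the entry for version 1.2. Later entries bring the SAP to the draft of amendment 03 and add the EN sample size and nivolumab dose intensity, so EN was in view while the rule stayed.

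A reader might infer that EN violations go undetected altogether. The documents do not support that: an EN subject with exactly 3 lines is flagged, and the measurable-disease item works in both cohorts. What the rule misses is EN subjects with 0 to 2 lines; in addition, no listed item checks the required drug classes.

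A reader might also infer that the ORR or PFS results are distorted. They are not. SAP 7.1 runs efficacy and safety on all treated subjects, a set defined by receipt of elotuzumab. The ITT set in SAP 6.3 and 7.3 depends on meeting eligibility criteria, but the SAP does not say this flag derives it, and the efficacy and safety analyses do not use it.

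Finally, 7.2.2 is a short programmed list and not a full eligibility audit. It does not check the EPd minimum of 1 line or the lenalidomide requirement either. That is a choice of scope, and those checks are not needed to remove the contradiction.

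**Conclusion.** The rule is wrong as written for EN. It contradicts protocol 3.3.1 by listing as deviators the EN subjects who satisfy the current line requirement, and it passes over those with 0 to 2 lines. The size is up to 30 of about 30 planned EN subjects falsely flagged. This assumes that the item is programmed literally, that all were enrolled under the current criterion, and that all met it. SAP 2.1 still gives about 25 EN subjects; the 100% EN proportion would be the same with that number.

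The consequence is limited to one table and listing. It is a reporting inconsistency between protocol and SAP, with no effect on any efficacy or safety estimate or interval. It deserves correction because the output is topline and the SAP reserves it for deviations that bear on interpretation.

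**What to change.** Replace the single prior-lines item in SAP 7.2.2 with two:
- EPd: more than 2 prior lines.
- EN: fewer than 4 prior lines and, where the coded prior-therapy eCRF data allow, no prior proteasome inhibitor, no prior immunomodulatory agent or no prior anti-CD38 antibody.

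State that each subject is judged by the cohort entered at enrolment, so that an EN subject who later crosses over to EPd keeps the EN criterion. State also that the protocol version in force at enrolment applies, since Revised Protocol 03 changed the EN requirement. Leave the measurable-disease item as it is.

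The cost is a change of SAP wording and a cohort-dependent programming condition. SAP 7.3.2 already summarises lines of prior therapy, and SAP 7.3.4 codes prior systemic therapy from its own eCRF page, so the line counts should need no new data collection. The drug-class check takes somewhat more programming and depends on how completely that page was filled in.
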